
Discontinuation rules
	
Discontinuation of the whole trial
 
 • The trial will be stopped in case of unacceptable toxicity. Unacceptable toxicity is found if more than 2 of the first 30 patients in one of the arms of the trial die from acute complications of therapy. • Additionally, the DMSB and/or the coordinating investigator as the designee of the sponsor can stop the trial transiently or permanently for any safety reason. • There is no interim analysis for efficacy. Thus there is no stopping rule based on efficacy parameters. 
Discontinuation rules for an individual patient. An individual patient will be discontinued from study therapy under the following circumstances:
 
 • There is MRI- defined progressive disease according to modified RANO criteria. • The patient requests discontinuation (as long as the patient consents explicitly for further follow-up): 
 ▪ Non-compliance of the patient • The drugs exhibit unacceptable toxicity: 
 Delay of the next course for 6 weeks or more due to hematological toxicity Any non-hematological CTCAE grade 3/4 toxicity attributable to CCNU or temozolomide. Those patients may receive temozolomide or CCNU monotherapy, respectively, if toxicity can be clearly attributed to one of the the agents • The patient becomes pregnant

Statistical analysis
	
Efficacy: Overall survival (OS) as primary efficacy parameter is measured from the day of randomization into one of the study arms until death. OS will be compared between the two treatment groups using a two-sided log-rank test at a level of 5% stratified for center and GBM recursive partitioning analysis (RPA) class.
 
Description of the primary efficacy analysis and population: The primary analysis will be performed according to the intention to treat (ITT) principle. The intent-to treat (ITT) analysis includes all 128 patients who have been randomized in the trial and have started with the first dose of CCNU (experimental arm) or TMZ

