2.3 End-points

Primary end-point:

- Overall survival (OS) as measured from the day of randomization until death
-

Secondary endpoints:

- Progression-free survival (PFS) as measured from the day of randomization until diagnosis of progressive disease determined by MRI (modified RANO criteria)
- Best response rate determined by MRI (modified RANO criteria)
- Frequency of delay of the next CCNU/TMZ or TMZ course by more than 2 weeks
- Acute toxicity during radiotherapy and chemotherapy according to CTC AE V4.0
- Quality of life, determined by EORTC QLQ questionnaires
- Evaluation of late neurotoxicity by MMSE and NOA-07 test battery.
- Time to treatment failure

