3.6 Patients Replacement

According to the patient number calculation, 136 patients have to be allocated and 128 of these allocated patients are expected to form the intention-to-treat (ITT) population which included all patients who are included in the trial and have received their first dose of chemotherapy. This implies that about 6% of the patients (n=8) included in the trial are anticipated to be drop-outs before starting chemotherapy. These drop-out patients are not replaced.

Any patient dropping out after receiving his first dose of chemotherapy is part of the ITT population and is not replaced.

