4. TRIAL DESIGN

This is a multicenter, randomized, open-label phase III trial for newly diagnosed glioblastoma patients with methylated MGMT promoter in their tumor. The study includes the following steps:

Screening phase (1-3 weeks after resection): Patients with previously untreated GBM are screened for the trial. After obtaining informed consent for determination of MGMT promoter methylation status and reference neuropathology, a block of paraffin-embedded tissue is sent for reference neuropathology review to the Department of Neuropathology, University of Bonn. From there, tissue is sent to MDxHealth, where the MGMT promoter methylation status is determined by methylation-specific PCR.

Baseline and randomization phase (week 3-5 after resection): Baseline examinations are performed. After obtaining the MGMT promoter status and confirmation of GBM histology (for the form to submit reference neuropathology and MGMT testing see appendix 3) and obtaining informed consent for trial participation, inclusion/exclusion criteria are evaluated and documented, patients are randomized for standard TMZ chemotherapy or experimental CCNU/TMZ therapy, both in combination with standard RT. Therapy (i.e. RT) has to start within 2 weeks after randomization and 5 weeks after surgery. A 5 week interval is generally accepted for clinical trials in GBM and does not impair therapeutic efficacy (Blumenthal et al., 2008).

Treatment phase: The treatment phase as well as the follow-up phase of the trial is summarized in figure 1. The treatment phase should start not later than 5 weeks after surgery and not later than 2 weeks after randomization and baseline visit.

[figure not shown]
The trial includes two treatment arms:

Experimental arm (CCNU/TMZ arm; 50% of patients): the first course of CCNU (100 mg/m² day 1) and TMZ (100 mg/m²/day, day 2-6) is started on the first day of RT (60 Gy in 2 Gy fractions, 5 days/week). The following 5 courses are applied 6 weeks after the start of the previous course. In the experimental arm, not more than 6 six week courses can be applied.

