Standard arm (TMZ arm; 50% of patients): the first application of TMZ is given on the first day of RT (60 Gy in 2 Gy fractions, 5 days/week). During RT, TMZ is given on a daily base with 75 mg/m²/day (including RT-free weekend days). RT with concomitant TMZ chemotherapy (6 weeks) is followed by a 4 weeks interval without therapy. In week 11 after the initiation of RT, the TMZ block chemotherapy ensues with 6 courses of TMZ 150-200 mg/m² day 1-5 of a 28 day course. It is recommended that TMZ chemotherapy is stopped after application of 6 courses (as suggested by Stupp et al., 2005).

Follow-up phase: After the end of the treatment phase, all patients will be followed by clinical examination and contrast-enhanced MRI every 12 weeks until 3 years after randomization. Follow-up of all patients ends 36 months after the inclusion of the last patient. All patients in the trial are followed until this time point.

Fig.1: Schematic overview of the study

* Laboratory and Clinical examinations, toxicity recording as detailed in table 1

- TMZ 75 mg/m² p.o./die over 6 weeks during RT
- TMZ 150 D200 mg/m² p.o. day 1 D5 of a 28 day course
- Radiotherapy of the tumor region, daily, 30 x 2 Gy
Total dose 60 Gy
- CCNU 100 mg/m² p.o. on day 1 +
TMZ 100 mg/m² p.o./die day 2 -6 of 42 day course

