6.2.2 Definition and evaluation of efficacy endpoints

Overall survival (Primary endpoint): Survival is defined as the duration from randomization to the date of death due to any cause.

Progression-free survival: The progression-free survival is defined as the time from randomization to the first documented evidence of progression of disease according to the modified RANO criteria.

Overall Response: The overall response rate is defined as the relative proportion of patients with complete and partial responses.

Time to Treatment Failure: Time to treatment failure is defined as the duration from the day of diagnosis (surgery obtaining histology) to any of the following:

- Death for any reason
- relapse or progressive disease (PD) during or after study treatment,
- discontinuation of combined CCNU/TMZ treatment for any reason before the completion of 3 cycles CCNU/TMZ

Frequency of delay of the next CCNU/TMZ or TMZ course by more than 2 weeks

Quality of Life: The EORTC QoL questionnaire modules QLQ-C30 and BN20 will be used to assess the quality of life. These assessments will be performed on the visits specified in the Time and Events Schedule. Patients will be given these questionnaires to complete by a study center staff member. The staff member will collect each completed assessment and check it for completeness before giving the patient the next assessment to complete.

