9.3 Statistical and Analytical Methods: Efficacy parameters

Statistical analysis starts 36 months after the inclusion of the last patient. Statistical analysis will be performed at the Institute of Medical Biometry, Informatics and Epidemiology (IMBIE) at the University of Bonn Medical Center (Dir.: [name]. [name]). OS, the primary parameter, will be compared between treatment groups using a two-sided log-rank-test at a level of 5% stratified for center and for RPA class. Centers contributing less than 3 patients for one arm of the treatment arms are pooled in this analysis. The primary confirmatory analysis will be based on the intention-to-treat (ITT) population. The ITT population contains all patients who have received a first dose

of chemotherapy (CCNU in the experimental arm and TMZ in the standard arm). Dropouts will be evaluated as censored observations at the time of dropout. An additional comparison will be made based on the per protocol population. The results of both analyses should be consistent. The per-protocol analysis includes all patients who have received two courses of CCNU/TMZ in the experimental arm or concomitant TMZ plus one course of adjuvant TMZ in the standard arm. Additionally, an analysis of the “as randomized” population will be performed.

The following secondary efficacy endpoints are also determined:

- Progression-free survival (PFS) determined by MRI (modified RANO criteria)
- Best response rate determined by MRI (modified RANO criteria)
- Frequency of delay of the next CCNU/TMZ or TMZ course by more than 2 weeks
- Acute toxicity during radiotherapy and chemotherapy according to CTC AE V4.0
- Quality of life, determined by EORTC QLQ questionnaires
- Evaluation of late neurotoxicity by MMSE and NOA-07 test battery

Survival parameters are measured in days starting from the day of start of treatment (first day of RT). Surviving patients and patients lost for follow-up are censored for the Kaplan-Meier analysis. Overall survival and progression-free survival will be summarized by Kaplan-Meier curves. Median time estimates as well as associated 95% confidence intervals will be reported. In addition Cox regression analyses adjusted and unadjusted for stratification factors such as age, performance score, extent of resection will be performed in an exploratory manner. The analysis will be based on the intent-to-treat population and repeated for the per-protocol population.

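### Section 9.3 starts the survival clock at the first day of radiotherapy, while every endpoint definition in the protocol starts OS and PFS at randomization

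*Protocol*

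**What the plan says.** OS starts at randomization in four places. The Synopsis (Primary Endpoint) and Section 2.3 use the same words: "Overall survival (OS) as measured from the day of randomization until death". The Synopsis text on statistical analysis says that OS "is measured from the day of randomization into one of the study arms until death". Section 6.2.2 says: "Survival is defined as the duration from randomization to the date of death due to any cause". PFS also starts at randomization, in the Synopsis list of secondary endpoints, in Section 2.3 and in Section 6.2.2, where it is "defined as the time from randomization to the first documented evidence of progression of disease".

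Section 9.3, after the list of secondary efficacy endpoints, opens its paragraph on survival summaries with: "Survival parameters are measured in days starting from the day of start of treatment (first day of RT". The same paragraph goes on to name OS and PFS for the Kaplan-Meier curves, the medians and the Cox models.

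The two dates can differ. Section 4 says: "Therapy (i.e. RT) has to start within 2 weeks after randomization and 5 weeks after surgery". Chemotherapy begins on the same day as radiotherapy. In the standard arm "the first application of TMZ is given on the first day of RT", and the first CCNU/TMZ course follows the same rule. Section 9.3 restricts the population it calls ITT to patients given a first dose of chemotherapy, and it also promises an analysis of the population as randomized. Section 3.6 expects that "about 6% of the patients (n=8) included in the trial are anticipated to be drop-outs before starting chemotherapy".

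**The concern.** A confirmatory endpoint needs one time origin. Here the analysis section disagrees with the endpoint definitions and does not mark its clock as a sensitivity analysis. Two things follow if Section 9.3 is applied as written.

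First, time zero becomes an event after allocation. Section 9.2 states that patients and physicians cannot be blinded, so the arm is known while radiotherapy is being arranged. If the delay differs between arms, the arm with the longer delay loses more of its survival time, and randomization no longer protects the comparison from that.

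Second, the as-randomized analysis is the only one meant to keep everyone allocated. A patient who is never irradiated has no first day of radiotherapy, and a patient who dies before it has no valid time. The check on the treated-only primary analysis would then drift back towards the same treated patients.

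Two definitions also leave a choice that could be made after outcomes are known.

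**Working it through.** **1. The origins side by side.**

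| Place in protocol | OS | PFS |
|---|---|---|
| Synopsis, endpoints | randomization | randomization |
| Synopsis, statistical analysis | randomization | not stated |
| Section 2.3 | randomization | randomization |
| Section 6.2.2 | randomization | randomization |
| Section 9.3 | first day of RT | first day of RT |

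The assessment schedule also follows randomization: MRI visits run every 12 weeks from it (Section 6.1), and the later pseudoprogression rule ends at the visit 24 weeks after it (Section 6.2.1).

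**2. Largest permitted shift.** Two weeks (Section 4) = 14 days; 14 / 30.4375 = 0.46 months. Each survival time is shortened by at most that amount, and the median moves by about that amount at most.

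**3. Patients without a time zero in the as-randomized analysis.** 136 − 128 = 8, and 8 / 136 = 5.9% (Sections 3.6 and 9.1). This is an upper figure, because it counts drop-outs before chemotherapy and some of them may still be irradiated. Section 9.1 itself says 6% may be too high. It cites 0 of 31 in the phase II trial and 9 of 573 (1.6%) refusing further involvement in the earlier standard-arm trial; 136 × 9/573 = 2.1 patients. A fair range is 0 to 8.

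**4. Deaths that could fall in the gap.** The exponential rates implied by Section 9.1 are −ln(0.489)/2 = 0.358 and −ln(0.70)/2 = 0.178 per year (the protocol prints 0.356 and 0.176). With d = 14/365.25 years, 1 − exp(−λd) = 0.0136 and 0.0068. For 68 patients per arm: 68 × 0.0136 + 68 × 0.0068 = 1.4 deaths. With the observed pooled rate of 0.1994: 136 × 0.0076 = 1.0. Both assume that every gap is the full 14 days. Section 3.2 requires an estimated life expectancy of at least 12 weeks, so the true number is probably lower.

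**5. Effect on the comparison.** The planned figure was reproduced first. With 64 patients per arm, R = 2 years of recruitment and F = 2 years of follow-up, the expected number of deaths is the sum over arms of 64 × [1 − (exp(−λF) − exp(−λ(R+F)))/(λR)] = 67.96, against 68 in the protocol. Schoenfeld power at that number is 81.8%, against 80% stated.

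The log-rank test was then simulated 4,000 times on each clock. The gap was assumed uniform on 0 to 14 days and equal in both arms, and patients who died inside the gap were dropped from the radiotherapy clock.

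| Follow-up | Power, randomization clock | Power, RT clock | Trials with opposite verdicts |
|---|---|---|---|
| 2 years | 81.1% | 80.7% | 2.1% |
| 3 years | 88.2% | 88.0% | 1.4% |

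The simulated test was unstratified, whereas the planned one is stratified by center and RPA class. Unequal delays were not simulated.

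**The case against.** The best defence is that the Section 9.3 sentence has a narrower scope. It opens a paragraph on descriptive curves and exploratory Cox models that ends by naming the ITT and per-protocol populations. Both consist of treated patients, who have a radiotherapy date under the schedule, and in a treated-only set a clock starting at treatment is coherent. The log-rank test and the as-randomized analysis stand in an earlier paragraph, and the Synopsis text that specifies the log-rank test counts from randomization. A fuller analysis plan is promised and may settle the matter.

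Part of this stands. The layout makes the narrow reading possible, and no fault in an unseen analysis plan can be assumed. But the sentence speaks of survival parameters in general, and its paragraph names OS and PFS. Even on the narrow reading, the Kaplan-Meier medians of the primary endpoint would run from a different origin than its definition.

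A reader might also infer more than the documents support:

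- **That the as-randomized analysis becomes impossible.** It does not. Only patients who never start radiotherapy, or who die before it, are affected.
- **That 8 to 13 patients have no time origin.** The 8 is a planning allowance for loss before chemotherapy, not before radiotherapy. The 13 comes from subtracting 128 from the Synopsis figure of 141, which conflicts with 136 elsewhere; nothing says that 13 patients never start.
- **That the clock removes early deaths from the primary test.** The ITT definition already excludes patients who die before a first dose, under either clock.

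**Conclusion.** Section 9.3 is wrong as written: it contradicts the randomization origin stated for OS in four places and for PFS in three. The matter is one of definition and pre-specification of the primary endpoint. The planned 68 events and 80% power are unaffected.

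With similar delays in both arms the effect is small: under half a percentage point of power, with opposite significance verdicts in about 1.4% to 2.1% of simulated trials. That rests on exponential survival and the assumed equal uniform gap. A difference in delay between arms is possible, but the permitted delay is capped at 14 days and the documents give no figure for such a difference. In the as-randomized analysis, between 0 and about 8 of 136 patients would lack a valid time, the upper end holding only if none of the expected drop-outs before chemotherapy is irradiated.

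The reason to act is that the definition should be settled before outcomes are known, not that a large bias has been shown.

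**What to change.** Replace the sentence in Section 9.3 with: *OS and PFS are measured in days from the date of randomization in all analysis populations.* If time from the start of radiotherapy is of interest, list it only as a sensitivity analysis in treated patients.

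The cost is one sentence in the protocol, plus a check that the analysis plan uses the same origin. The endpoint definitions already require the randomization date, so no new data and no change to the sample size are needed. The change does not bring untreated patients into the primary ITT set; that set's definition is a separate matter. Time to treatment failure, which Section 6.2.2 counts from the day of surgery, is a third origin and should be reviewed separately.

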9.4 Safety Analysis

Patients who did not receive at least one dose of any study medication will be excluded from the analysis of safety. Tables of adverse event incidence (preferred term classification) and individual incidence will be produced. A complementary analysis of adverse events by severity of event and by relationship to trial treatment will also be performed. Dose reductions, delay of therapy in subsequent courses ("Frequency of

delay of the next CCNU/TMZ or TMZ course by more than 2 weeks” as secondary endpoint) and premature withdrawals will also be described.

9.5 Assessment of Quality of life and late neurotoxicity

Quality of life (QoL) is recorded through the standardized and validated EORTC QLQ-C30 and BN20 questionnaires (Osoba et al., 1996). These questionnaires contain a total of 30 QoL-related questions which are scored on a nominal scale (0-5 points); the result of each question is recorded for computerized examination and the questions relating to the same dimension of QoL (e.g. emotional well-being) are taken together for an overall score of this dimension. The scores for the different dimensions will be compared between repeated assessments throughout the trial and between the two arms of the trial.

MMSE is recorded as a point score with a maximum of 30 points. Values above 26 points are regarded as normal. The short neuropsychological test *The NOA-07 test battery* tests the performance in the 4 following neuropsychological dimensions:

1. Attention as measured by the Trail Making test B (Lezak et al. 1995),
2. Working memory as determined by the module “figure repeating” of the HAWIE-R test (Tewes et al., 1994),
3. visoperceptive performance as determined by the Trail making test A (Lezak et al., 1995) and
4. alphabetic (controlled Oral Word association Test COWA, Benton and Hamsher, 1989) and semantic verbal fluency (Lezak et al., 1995).

The scores for the different dimensions will be compared between repeated assessments throughout the trial.

10. INVESTIGATIONAL PRODUCT LOGISTICS

CCNU and TMZ are both commercially available drugs approved for marketing authorization in Germany. Therefore the capsules are prescribed by the treating physician and provided by the local pharmacy. Drugs are to be kept in an appropriate, secure, locked area at the pharmacy of the participating center and are supplied on the day of intake by the pharmacy. CCNU will be taken by the patient in the hospital under supervision of study personnel. TMZ (day 2-6 of each course) is distributed by the trial center and taken on an outpatient base. The health insurance will be charged for the standard treatment whereas the chemotherapy given in the experimental arm will be covered by the trial organisation. The investigator, or a responsible party designated by

the investigator, will maintain a careful record of the inventory and disposition of all drugs received using the Drug Accountability Record form. Since this is an open study and drugs are approved for marketing authorization no labelling will be performed.

11. ETHICAL AND REGULATORY ASPECTS

The patients in the standard arm receive the current standard therapy of primary GBM therapy. The regimen used for the experimental arm is well supported by previous phase II data ([name] et al., 2006, Glas et al., 2009). According to the non-randomized phase II data, the patients in the experimental CCNU/TMZ arm may have more myelotoxicity which may be balanced by the expected superior efficacy. The patients in the standard arm will undergo up-to date standard therapy without frequent and severe myelotoxicity. All trial participants will receive superior neurooncological care (e.g. frequent MRI and clinical follow-up by an experienced team) as compared to community standards, i.e. patients may realize benefits from participation in the trial even if they are randomized to the standard arm.

All investigators are responsible for ensuring that the clinical study is performed in accordance with the protocol, current ICH guidelines on Good Clinical Practice (GCP), and applicable regulatory requirements.

GCP is an international ethical and scientific quality standard for designing, conducting, recording, and reporting studies that involve the participation of human subjects. Compliance with this standard provides public assurance that the rights, safety, and well-being of study subjects are protected, consistent with the principles that have originated in the Declaration of Helsinki, and that the clinical study data are credible.

